3.2 Exclusion Criteria

Patients should not enter the study if any of the following exclusion criteria are fulfilled:

1. Locally advanced lung cancer candidate for curative treatment through radical surgery and/or radio(chemo)therapy.
2. Patients diagnosed with another lung cancer subtype, patients with mixed NSCLC with predominantly squamous cell cancer, or with any small cell lung cancer component.
3. Patients with an EGFR exon 20 insertion.
4. Patients with just one measurable or evaluable tumour lesion that has been resected or irradiated prior to their enrolment in the study.
5. Second active neoplasia.
6. Treatment with an investigational drug within five half-lives of the compound.
7. Participation in another clinical study with an IP during the last 3 weeks before the first day of study treatment.
8. Patients who have received prior immunotherapies.
9. Patients who have received prior EGFR treatments for lung cancer.
10. Patients who have received prior treatment with an EGFR TKI including in the adjuvant setting.
11. Patients who have received previous treatment for metastatic or stage IV disease.

12. Prior treatment with cytotoxic chemotherapy for advanced NSCLC (neoadjuvant/adjuvant chemotherapy is permitted if at least 6 months have elapsed between the end of chemotherapy and the first day of study treatment).
13. Patients with a history of cancer that has been completely treated, with no evidence of malignant disease currently cannot be enrolled in the study if their chemotherapy was completed less than 6 months prior and/or have received a bone marrow transplant less than 2 years before the first day of study treatment.
14. Any unresolved toxicities from prior therapy greater than CTCAE Grade 1 at the time of starting study treatment with the exception of alopecia and Grade 2, prior platinum-therapy related neuropathy.
15. Any evidence of severe or uncontrolled systemic diseases, including uncontrolled hypertension and active bleeding diatheses, which in the Investigator's opinion makes it undesirable for the patient to participate in the trial or which would jeopardise compliance with the protocol, or active infection (eg, patients receiving treatment for infection) including hepatitis C and human immunodeficiency virus (HIV), or active uncontrolled Hepatitis B virus (HBV) infection.
 - Screening for chronic conditions is not required.

Should patients with HBV infection be included, patients are only eligible if they meet all the following criteria:

- Demonstrated absence of HCV co-infection or history of HCV co-infection.
- Demonstrated absence of HIV infection.
- Patients with active HBV infection are eligible if they are:
 - Receiving anti-viral treatment for at least 6 weeks prior to study treatment, HBV DNA is suppressed to < 100 IU/mL and transaminase levels are below upper limit of normal (ULN).
- Patients with a resolved or chronic infection HBV are eligible if they are:
 - Negative for HBsAg and positive for hepatitis B core antibody [anti-HBc IgG]. In addition, patients must be receiving anti-viral prophylaxis for 2 to 4 weeks prior to study treatment.

or

- Positive for HBsAg, but for > 6 months have had transaminases levels below ULN and HBV DNA levels below < 100 IU/mL (ie, are in an inactive carrier state). In addition, patients must be receiving anti-viral prophylaxis for 2 to 4 weeks prior to study treatment. Refer to Section [3.5](#).

Should patients with HIV infection be included, patients are only eligible if they meet ALL of the following criteria:

- Undetectable viral RNA load for 6 months
- CD4+ count of > 350 cells/ μ L
- No history of AIDS-defining opportunistic infection within the past 12 months
- Stable for at least 4 weeks on the same anti-HIV medications.

16. Patients who have had a surgical procedure unrelated to the study within 14 days or major surgery within 1 month prior to the administration of the study drug; patients with a significant traumatic lesion (as judged by the Investigator that would risk patient safety) during the 4 weeks prior to starting the administration of the study drug; patients who have not recovered from the side effects of any major surgery; or patients who might need major surgery during the course of the study.
17. Past medical history of ILD, drug-induced ILD, radiation pneumonitis which required corticosteroid treatment, or any evidence of clinically active ILD.
18. Any of the following cardiac criteria:
 - Mean resting QT interval corrected for heart rate (QTc) > 470 msec, obtained from 3 ECGs, using the screening clinic ECG machine-derived QTc value.
 - Any clinically important abnormalities in rhythm, conduction or morphology of resting ECG, eg, complete left bundle branch block, third-degree heart block, and second-degree heart block.
 - Any factors that increase the risk of QTc prolongation or risk of arrhythmic events such as heart failure, hypokalaemia, hypomagnesaemia, hypocalcaemia, congenital long QT syndrome, family history of long QT syndrome or unexplained sudden death under 40 years of age in first degree relatives or any concomitant medication known to prolong the QT interval.
19. Spinal cord compression, symptomatic and unstable brain metastases except for those patients who have completed definitive therapy and have had a stable neurological status for at least 2 weeks after completion of definitive therapy. Patients may be on corticosteroids to control brain metastases if they have been on a stable dose for 2 weeks (14 days) prior to the start of study treatment and are clinically asymptomatic.

20. Refractory nausea and vomiting, chronic gastrointestinal diseases, inability to swallow the formulated product or previous significant bowel resection that would preclude adequate absorption of osimertinib.
21. Inadequate bone marrow reserve or organ function as demonstrated by any of the following laboratory values:
 - Absolute neutrophil count $< 1.5 \times 10^9/\text{L}$.
 - Platelet count $< 100 \times 10^9/\text{L}$.
 - Haemoglobin (Hb) $< 90 \text{ g/L}$.
 - Alanine aminotransferase (ALT) > 2.5 times the ULN if no demonstrable liver metastases or > 5 times ULN in the presence of liver metastases.
 - Aspartate aminotransferase (AST) > 2.5 times ULN if no demonstrable liver metastases or > 5 times ULN in the presence of liver metastases.
 - Total bilirubin (TBL) > 1.5 times ULN if no liver metastases or > 3 times ULN in the presence of documented Gilbert's Syndrome (unconjugated hyperbilirubinaemia) or liver metastases.
 - Creatinine > 1.5 times ULN concurrent with creatinine clearance $< 50 \text{ mL/min}$ (measured or calculated by Cockcroft and Gault equation); confirmation of creatinine clearance is only required when creatinine is > 1.5 times ULN.
22. Female patients who are breastfeeding.
23. Patients currently receiving (or unable to stop use prior to receiving the first dose of study treatment) medications or herbal supplements known to be potent inducers of cytochrome (CYP) 3A4 (at least 3 weeks prior; [Appendix E](#)). All patients must try to avoid concomitant use of any medications, herbal supplements, and/or ingestion of foods with known inducer effects on CYP3A4.
24. Patient unwilling to undergo a biopsy at the time of disease progression.
25. History of hypersensitivity to active or inactive excipients of osimertinib or drugs with a similar chemical structure or class to osimertinib.
26. Judgement by the Investigator that the patient should not participate in the study if the patient is unlikely to comply with study procedures, restrictions, and requirements.
27. Involvement in the planning and/or conduct of the study (applies to both AstraZeneca staff and/or staff at the study site).

28. Previous enrolment in the present study.

For procedures for withdrawal of incorrectly enrolled patients see Section [3.4](#).

3.3 Patient Screening and Enrolment

Investigators should keep a record, the patient screening log, of patients who entered pre-study screening.

The Investigators will:

1. Determine patient eligibility (see Section [3.1](#) and Section [3.2](#)).
2. Obtain signed informed consent from the potential patient or their guardian/legal representative before any study specific procedures are performed.
3. Assign potential patient a unique enrolment number, beginning with 'E#' (generated in the Interactive Voice Response System/Interactive Web Response System [IVRS/IWRS]).

If a patient withdraws from participation in the study, then his/her enrolment code cannot be re-used.

3.4 Procedures for Handling Incorrectly Enrolled Patients

Patients who fail to meet the eligibility criteria should not, under any circumstances, be enrolled or receive study medication. There can be no exceptions to this rule. Patients who are enrolled, but subsequently found not to meet all the eligibility criteria must not be initiated on treatment, and must be withdrawn from the study.

Where a patient does not meet all the eligibility criteria but is enrolled in error, or incorrectly started on treatment, the Investigator should inform the AstraZeneca Study Physician immediately, and a discussion should occur between the AstraZeneca Study Physician and the Investigator regarding whether to continue or discontinue the patient from treatment. The AstraZeneca Study Physician must ensure all decisions are appropriately documented.

3.5 Restrictions

The following restrictions apply while the patient is receiving study treatment and for the specified times before and after:

1. Females of childbearing potential should use highly effective methods of contraception from the time of screening until 6 weeks after discontinuing study treatment. Highly effective methods are provided in [Appendix G](#).
2. Male patients should be asked to use barrier contraceptives (ie, by use of condoms) during sex with all partners of childbearing potential during the trial and for a

washout period of 4 months. Female partners (of childbearing potential) of male patients must also use a highly effective method of contraception throughout this period. Male patients should avoid procreation for 4 months after completion of study treatment. Patients should refrain from donating sperm from the start of dosing until 4 months after discontinuing study treatment.

3. Once enrolled, all patients must try to avoid concomitant use of medications, herbal supplements, and/or ingestion of foods that are known to be strong inducers of CYP3A4 whenever feasible, but patients may receive any medication that is clinically indicated for treatment of AEs. Such drugs must have been discontinued for an appropriate period before they enter screening and for a period of 3 weeks after the last dose of osimertinib. All concomitant medications should be captured on the electronic case report form (eCRF). Guidance on medicines to avoid, medications that require close monitoring, and on washout periods is provided (see [Appendix E](#)).
4. If medically feasible, patients taking regular medication, with the exception of potent inducers of CYP3A4 (see above), should be maintained on their regular medication throughout the study period. Patients taking concomitant medications whose disposition is dependent upon Breast Cancer Resistance Protein (BCRP) and/or P-glycoprotein (P-gp), and which have a narrow therapeutic index should be closely monitored for signs of changed tolerability as a result of increased exposure of the concomitant medication while receiving osimertinib. Guidance on medications to avoid, medications that require close monitoring and on washout periods is provided (see [Appendix E](#)).

Patients taking rosuvastatin should have creatine phosphokinase levels monitored (due to BCRP-mediated increase in exposure). If the patient experiences any potentially relevant AEs suggestive of muscle toxicity including unexplained muscle pain, tenderness, or weakness, particularly if accompanied by malaise or fever, rosuvastatin must be stopped and any appropriate further management should be taken.

Patients who have received prior treatment with immune-oncology (IO) therapies should be closely monitored for an appropriate period of time after the last dose of the IO treatment, in accordance with the respective IO label, as immune-mediated adverse reactions with the IO therapy may occur at any time during or after discontinuation of therapy. The stop date of the prior IO drug therapy should be captured in the eCRF.

5. Patients should receive HBV anti-viral prophylaxis post treatment as determined by their hepatologist.
6. In patients with resolved or chronic hepatitis B infection (inactive carrier state) or active controlled HBV infection on treatment with osimertinib:

- Recommend monthly monitoring of ALT/AST, HBV DNA levels and HBsAg (if negative at baseline)
- Where liver signs and symptoms of viral reactivation appear (HBV DNA levels exceeding 10-fold from baseline or ≥ 100 IU/mL (if baseline HBV DNA levels are undetectable) or conversion of HBsAg negative to positive):
 - Expert hepatologist/specialist oversight of the patient is required
 - Consider interruption or discontinuation of study treatment, based on risk-benefit assessment.

7. In patients with HIV, viral RNA load and CD4 + cell count should be monitored per local SoC (eg, every 3 months).

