Appendix E Guidance Regarding Potential Interactions with Concomitant Medications

The use of any natural/herbal products or other “folk remedies” should be discouraged, but use of these products, as well as use of all vitamins, nutritional supplements, and all other concomitant medications must be recorded in the eCRF.

E 1 Drugs inducing CYP3A4 metabolism that AstraZeneca strongly recommends are not combined with osimertinib

Osimertinib is metabolised by CYP3A4 and CYP3A5 enzymes.

A drug-drug interaction study of osimertinib evaluated in patients showed that there is potential for osimertinib being a victim when co-administered with strong inducers of CYP3A4 (osimertinib concentrations are decreased when co-dosed with rifampicin).

The following potent inducers of CYP3A4 must not be used during this study for any patient receiving osimertinib.

Table E1 Drugs Inducing CYP3A4

Contraindicated drugs	Withdrawal period prior to osimertinib start
Carbamazepine, phenobarbital (phenobarbitone), phenytoin, rifampicin, rifabutin, rifapentine, St John's Wort	3 weeks

This list is not intended to be exhaustive, and a similar restriction will apply to other agents that are known to strongly modulate CYP3A4 activity. Appropriate medical judgement is required. Please contact AstraZeneca with any queries you have on this issue.

Medicines whose exposures may be affected by osimertinib that AstraZeneca considers may be allowed with caution

Osimertinib may increase the concentration of sensitive BCRP and P-gp substrates (concentration of the sensitive BCRP substrate, rosuvastatin and sensitive P-gp substrate, fexofenadine, are increased).

Table E2 Exposure, Pharmacological Action and Toxicity May be Increased by Osimertinib

Warning of possible interaction	Advice
Rosuvastatin	Drugs are permitted but caution should be exercised and patients monitored closely for possible drug interactions. Please refer to full prescribing information for all drugs prior to co-administration with osimertinib.
Sulfasalazine	
Doxorubicin	
Daunorubicin	
Topotecan	
Dabigatran	
Aliskiren	
Digoxin	

E 2 Drugs that prolong QT interval

The drugs listed in this section are taken from information provided by The Arizona Center for Education and Research on Therapeutics on the CredibleMeds® website <https://www.crediblemeds.org/>. The website categorises drugs based on the risk of inducing Torsades de Pointes (TdP).

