2.2 Protocol deviations

The following general categories will be considered important protocol deviations which will be listed and discussed in the clinical study report (CSR) as appropriate for the study:

- Informed consent procedure deviation (eg, no informed consent signed prior to any screening procedure)
- Eligibility criteria deviation (eg, any inclusion criteria not met or exclusion criteria met)
- Received prohibited concomitant medications (or unable to stop use prior to receiving the first dose of study drug) or herbal supplements known to be potent inducers of cytochrome P450 (CYP) 3A4 (at least 3 weeks prior). Please refer to protocol Section 3.5 for those medications that are detailed as ‘not to be administered’ or being ‘restricted concomitant medications’. These will be used as a guiding principle for the physician review of all medications prior to database lock.
- Management of adverse events: Lack of prompt reporting of cases meeting Hy’s law criteria and serious adverse events (SAE) not being reported within 24 hours of awareness of the event.
- Tumour biopsy sample taken from lesion selected for RECIST assessment (unless only one lesion exists and the RECIST scans are performed within 14 days of screening biopsy).
- No baseline RECIST 1.1 assessment before start of treatment.
- RECIST 1.1 assessments not done every 8 weeks (± 7 days) in relationship to the date of first dose until RECIST 1.1 defined progression.
- Screening assessment not performed within 42 days prior to study drug initiation.

If the number of deviations which are considered to have the potential to impact the primary analysis is considered important, sensitivity analyses may be performed on subgroups. This will be decided during the data review meeting and before the database lock. The final classification of protocol deviations will be made prior to database lock. Any other deviations from monitoring notes or reports will be reported in an appendix to the CSR.

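### For a strong CYP3A4 inducer given to treat an on-study adverse event, Protocol Section 3.5 permits what Appendix E 1 forbids, and SAP 2.2 leans on Section 3.5 to define the deviation

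*Protocol*

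**What the plan says.** Protocol Section 3.5 item 3 sets the on-study rule and its exception in one sentence: enrolled patients are to try to avoid "strong inducers of CYP3A4 whenever feasible, but patients may receive any medication that is clinically indicated for treatment of AEs". The exception makes no reservation for inducers. The item ends by pointing to Appendix E, which it describes as guidance.

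Exclusion criterion 23 bars entry on potent inducers and adds a sentence about conduct: "All patients must try to avoid concomitant use of any medications, herbal supplements, and/or ingestion of foods with known inducer effects on CYP3A4".

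Appendix E 1 speaks in two strengths. Its heading reads "Drugs inducing CYP3A4 metabolism that AstraZeneca strongly recommends are not combined with osimertinib". The sentence above Table E1 is absolute: "The following potent inducers of CYP3A4 must not be used during this study for any patient receiving osimertinib". The table labels the listed drugs as contraindicated. The stated reason is that "osimertinib concentrations are decreased when co-dosed with rifampicin".

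SAP 2.2 lists receipt of prohibited medications or potent CYP3A4 inducers among the important protocol deviations. For the drugs concerned it says "Please refer to protocol Section 3.5 for those medications that are detailed as", followed by two labels, one for drugs that must not be given and one for restricted drugs. These serve as a guiding principle for physician review of all medications before database lock. Appendix E is not named.

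**The concern.** A site treating an AE needs one answer on whether a Table E1 drug may be used, and the protocol gives two. The interaction is one that the protocol itself says lowers osimertinib concentrations, so this is not a neutral formality.

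The second problem is in the SAP. An important-deviation category should let two people classify the same patient in the same way. Here the category is tied to a protocol section that has no list carrying the SAP's labels and that contains the very exception in dispute. The SAP wording also takes over pre-dose language from exclusion criterion 23 (inability to stop before the first dose, the three-week washout), so its reach over on-treatment use is not clear. Classification as an important deviation governs what is listed and discussed in the clinical study report, and it feeds the optional sensitivity analyses in SAP 2.2.

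**Working it through.** The plan gives no figure for inducer use, so the check is textual. Take one test case: a patient receiving osimertinib has an AE for which a Table E1 drug is clinically indicated.

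| Place | Rule | Result for the test case |
|---|---|---|
| Protocol 3.5 item 3 | Try to avoid where feasible; medication indicated for an AE is allowed | Permitted |
| Protocol 3.2, criterion 23, second sentence | Try to avoid; no AE exception and no ban | Discouraged |
| Appendix E 1, heading | Strong recommendation against | Discouraged |
| Appendix E 1, sentence above Table E1 | Not to be used in any patient on osimertinib | Forbidden |
| Protocol 7.7 and 7.7.1 | Refers to 3.5 and Appendix E; discretion only for other medication | Silent on which prevails |
| SAP 2.2 | Potent-inducer use is an important deviation, with Section 3.5 as guide | Deviation if the category wording or Table E1 is followed; arguably not if the AE exception is followed |

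**How far the conflict reaches.** At entry, criterion 23 bars potent inducers and Table E1 gives a withdrawal period; these point the same way. For regular medication, Section 3.5 item 4 excepts potent inducers from the instruction to maintain it. Outside AE treatment the passages differ in strength but not in direction. The direct contradiction is the AE case.

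**What changes with the passage read.**
- Whether the use is allowed: yes.
- Whether it is an important deviation: yes.
- Whether it can enter a deviation-based sensitivity analysis: yes, though SAP 2.2 makes that analysis optional.
- Membership of the primary analysis set (SAP 2.1.1): no. It depends on evaluable paired biopsies and their timing.
- PFS events (SAP 3.2.2.1): no. They depend on RECIST progression or death.

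**The plan's own numbers.** These are unaffected. Expected pairs are 103 × 0.70 × 0.70 = 50.5, against about 50 stated, and overall failure is 1 − 0.49 = 51%, as stated. Exact 95% intervals for 5/50, 15/50 and 25/50 are 3.3% to 21.8%, 17.9% to 44.6% and 35.5% to 64.5%, which match Table 6 to its rounding.

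**Scale, as illustration only.** Assume 1 to 3 of 50 patients in the primary analysis set took an inducer, carried no marker, and were set aside. A 30% marker moves from 15/50 to 15/49 = 30.6% or 15/47 = 31.9%. A 10% marker moves from 5/50 to 5/49 = 10.2% or 5/47 = 10.6%. The change is 0.2 to 1.9 percentage points. Both the count and the marker status are assumptions without a source in the documents.

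**The case against.** The best defence is that the SAP does not really depend on Section 3.5. SAP 2.2 names potent CYP3A4 inducers itself, Section 3.5 is only a guide for physician review, and items 3 and 4 of that section both refer to Appendix E, so Table E1 is one cross-reference away. Protocol 7.7.1 gives the investigator discretion only over medication not already covered. All concomitant medication is recorded in the eCRF. Timing also counts: Protocol 9.3 ends the study by Q2 2023 and the SAP's amendment history runs to September 2023, so a protocol clarification may come too late to change conduct at sites.

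Much of this stands. It confines the conflict to one case, and it answers the inference that inducer use would go unnoticed: the category names these drugs and a physician reviews all medications. It does not settle how that physician should class a use that Section 3.5 expressly permits. Following the cross-reference leads from a permission to a prohibition with no rule of precedence. The timing argument weakens the benefit of the protocol change but not of the SAP change, provided the database is not yet locked, because SAP 2.2 makes the final classification before lock.

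**Conclusion.** The inconsistency is real and is in current text. It concerns one situation, a strong inducer given for an on-study AE, and has two consequences: conflicting instructions to sites, and an important-deviation category that can be applied either way to the same use. This rests on the wording alone and needs no assumption about frequency.

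A reader might go further and infer that progressions on lowered exposure would be counted as acquired resistance, probably with no marker found, and would shift marker proportions by 2 points per patient (1/50), or 6 points for three (3/50). The documents do not support that. They give the direction of the exposure change with rifampicin, but not its size or duration, how often inducers were used, or any link to marker status. The 2-to-6-point figure is a ceiling that requires every exposed patient to have otherwise carried the same marker; the illustration above, with marker-negative patients, gives less than 2 points. Nor does the conflict change who is in the primary analysis set or who has a PFS event. No numerical effect is claimed.

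**What to change.** 1. The sponsor should reconcile Section 3.5 item 3, the conduct sentence in exclusion criterion 23, and both the heading and the text of Appendix E 1 into one rule. Which rule is right is a clinical decision on which no view is taken here.
2. SAP 2.2 should cite that reconciled rule and its drug list in place of the general reference to Section 3.5, and should state that the category covers on-treatment use not permitted by the rule.
3. Optionally, list the patients in the primary analysis set with recorded strong-inducer use before progression, so that the number is known.

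The cost is one protocol clarification and a sentence or two in the SAP. The optional listing needs no new data: concomitant medications are recorded in the eCRF (Protocol 3.5), coded with the WHO Drug Dictionary (Protocol 9.4) and already summarised by ATC class (SAP 4.2.7). The SAP change should be made before deviations are finally classified at database lock.
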